## **Appendix A. Responsibilities of the Clinical Investigator**

Clinical research studies sponsored by AbbVie are subject to the Good Clinical Practices (GCP) and local regulations and guidelines governing the study at the site location. In signing the Investigator Agreement in Section 14.0 of this protocol, the investigator is agreeing to the following:

[figure not shown]
1. Conducting the study in accordance with the relevant, current protocol, making changes in a protocol only after notifying AbbVie, except when necessary to protect the safety, rights or welfare of subjects.
2. Personally conducting or supervising the described investigation(s).
3. Informing all subjects, or persons used as controls, that the drugs are being used for investigational purposes and complying with the requirements relating to informed consent and ethics committees (e.g., independent ethics committee [IEC] or institutional review board [IRB]) review and approval of the protocol and amendments.
4. Reporting adverse experiences that occur in the course of the investigation(s) to AbbVie and the site director.
5. Reading the information in the Investigator's Brochure/safety material provided, including the instructions for use and the potential risks and side effects of the investigational product(s).
6. Informing all associates, colleagues, and employees assisting in the conduct of the study about their obligations in meeting the above commitments.
7. Maintaining adequate and accurate records of the conduct of the study, making those records available for inspection by representatives of AbbVie and/or the appropriate regulatory agency, and retaining all study-related documents until notification from AbbVie.
8. Maintaining records demonstrating that an ethics committee reviewed and approved the initial clinical investigation and all amendments.

9. Reporting promptly, all changes in the research activity and all unanticipated problems involving risks to human subjects or others, to the appropriate individuals (e.g., coordinating investigator, institution director) and/or directly to the ethics committees and AbbVie.
10. Following the protocol and not make any changes in the research without ethics committee approval, except where necessary to eliminate apparent immediate hazards to human subjects.

## Appendix C. Study Activities

### Treatment Period

Activity	Screening	Day 1 a	Wk 2	Wk 4	Wk 8 b	Wk 12 b	EOT*/Premature D/C b
Informed Consent c	X						
Medical History d	X	X					
Physical Exam e	X	X		X	X	X	X
Vital Signs, Weight, Height, Body Mass Index	X	X	X	X	X	X	X
ECG f	X		X f				
Pregnancy Test (serum [s] urine [u]) g	X (s)	X (u)		X (u)	X (u)	X (u)	X (u)
Hematology/Chemistry/Urinanalysis/Coagulation Panel h	X	X	X	X	X	X	X
FSH i	X						
HbsAg, Anti-HCV Ab, Anti-HIV Ab	X						
HCV Genotype and Subtype	X						
Historical Liver Biopsy or FibroScan assessment or Screening FibroTest, Discriminant Score or liver biopsy for liver cirrhosis j	X						
Longitudinal Fibrotest & APR k		X					
Child Pugh Score l	X						
HCC Assessment: Liver ultrasound m and Alpha fetoprotein m	X						X
Concomitant Medication Assessment	X	X	X	X	X	X	X
Adverse Event Assessment n			X	X	X	X	X
Study Drugs Dispensation		X		X	X o	X o	
Dispense/Collect/Review Study Drug Dosing Card and HIV-1 Medication Card (if applicable)	X w	X	X	X	X p	X p	X

Activity	Screening	Day 1 a	Wk 2	Wk 4	Wk 8 b	Wk 12 b	EOT*/Premature D/C b
Study Drug Accountability and/or Review of Study Drug Adherence			X	X	X	X	X
PK Sampling		X	X q	X	X	X	X
HIV RNA Samples f	X	X		X	X	X	X
Flow Cytometry f	X	X		X			X
HCV RNA Samples	X	X	X	X	X	X	X
Assignment of Subject Number via IRT s	X						
Enrollment		X					
HCV Resistance Sample t		X					
Patient Reported Outcome u		X					X
Palatability Questionnaire v			X				X

D/C = Discontinuation; EOT (End of Treatment) = Final Treatment Visit; Day 1 = Baseline Visit

- \* The EOT visit can be at Week 8, Week 12, or Week 16 in accordance with Section 5.1 and activities should be conducted that are located in the EOT column. Treatment duration will be assigned according to Subjects HCV genotype, cirrhosis and prior HCV treatment experience status.
- a. All procedures to be performed prior to first dose, with the exception of the PK sample which will be obtained 4 hours post-dose.
- b. The Week 8 study visits apply to all subjects whose treatment duration is 12 weeks and 16 weeks in accordance with Section 5.1. The Week 12 study visits apply to all subjects whose treatment duration is 16 weeks in accordance with Section 5.1. Subjects who prematurely discontinue the Treatment Period should return to the site to complete the Premature D/C Visit Procedures (preferably prior to the initiation of any other anti-HCV therapy).
- c. Parent(s)/guardian(s) need to sign an IRB/IEC approved informed consent for the study prior to performing any screening or study-specific procedures. Additionally an assent from the subject will be obtained to meet the institution's IEC requirements, as applicable.
- d. A complete medical history will be taken at Screening and will be updated at the Study Day 1 Visit prior to study drug administration and will serve as the Baseline for clinical assessment.
- e. A symptom-directed physical examination may be performed at any other visit, when necessary.
- f. ECG will be measured only in the intensive PK portion of both parts, prior to any blood collection procedures, excluding subjects in Japan.
- g. A positive urine pregnancy test requires a confirmatory serum test. (Refer to Section 5.3.1.1 [Pregnancy Test] for additional details.) Females who are experiencing menses or are nearing sexual maturation in the opinion of the PI or who are of childbearing potential should have urine pregnancy testing done through Post-Treatment Week 4. Females of non-childbearing potential (as defined per protocol Inclusion Criteria 3) at Screening do not require pregnancy testing.

- h. For non-cirrhotic subjects: Coagulation panel performed only at Day 1, at EOT/premature D/C, and as clinically indicated.  
For cirrhotic subjects: Coagulation panel is required at all treatment visits, including the EOT/premature D/C visit.
- i. FSH for all female subjects aged 9 to < 18 years old.
- j. Subjects with no history of cirrhosis who have not had a liver biopsy within 24 months prior to screening, or Fibroscan within 6 months prior to screening will have a screening FibroTest and APRI to determine the presence or absence of cirrhosis for the purpose of treatment assignment. Subjects who have a liver biopsy or FibroScan indicating cirrhosis at any time in the past will not need a Fibrotest and APRI to be performed at screening as evidence of cirrhosis.
- k. Perform a Fibrotest and APRI at Day 1 for any subject who did not have a FibroTest and APRI done during Screening.
- l. Applies only to subjects with cirrhosis. The Child-Pugh score will be calculated in the EDC RAVE system. Subjects who were considered to be non-cirrhotic at the Screening visit but identified as cirrhotic (according to definitions listed in Section 5.3.1.1) during the screening period will return to the site prior to the baseline visit for Child-Pugh assessment.
- m. HCC assessment for subjects with compensated cirrhosis only: Liver ultrasound will be performed at the screening visit. Subjects with a historical negative liver ultrasound, CT or MRI (within 3 months prior to screening) are not required to undergo a screening ultrasound.
- n. See specific information regarding the adverse event collection in Section 6.1.1.1.
- o. Study drugs are dispensed at Week 8 for subjects on 12 weeks of treatment and at Weeks 8 and 12 for subjects on 16 weeks of treatment.
- p. Dosing card is filled out with date and time (to the nearest minutes) of the 2 doses before PK draws in Part 1 and Part 2. Dosing cards should not be dispensed at Weeks 8 or 12 if those are EOT visits for the subject (Section 5.3.1.1).
- q. Intensive PK sampling will be done at Week 2 for the first approximately 12 subjects in each of the age groups and subjects in Japan participating in J-IPK (Section 5.3.2.1). Intensive PK samples will be collected at Week 2 visit at time points zero (0) and after two (2), four (4), six (6) and twelve (12) hours of drug intake. For subjects in Japan who will not participate in the J-IPK schedule, samples will be collected at Week 2 visit at time points zero (0) and after two (2) and four (4) hours of drug intake.
- r. Only applicable for HCV/HIV-1 co-infected subject.
- s. The Subject will retain the subject number throughout the course of the study.
- t. Resistance sample will be collected at Day 1. For a subject who meets virologic failure criteria, a resistance sample must be drawn at the confirmatory visit. If HCV RNA is < 1000 IU/mL in the sample collected at the confirmatory visit, another resistance sample will be collected in the following visit to ensure the HCV RNA is  $\geq$  1000 IU/mL.
- u. The PRO should be administered as the first study procedure.
- v. Only subjects in Part 2 will complete the palatability questionnaire, at Week 2 and EOT or premature discontinuation visit.
- w. Dispense HIV-1 Medication Card at screening, if applicable.

**Post Treatment Period**

Activity	PT Wk 4	PT Wk 12	PT Wk 24	PT Wk 36	PT Wk 48	PT Wk 96	PT Wk 144	Premature D/C
Vital Signs, Weight, Height, Body Mass Index	X	X	X	X	X	X	X	X
Urine Pregnancy Test a	X							X a
Longitudinal Fibrotest and APRI		X			X	X	X	X
Hematology/Chemistry/Urinalysis b /Coagulation Panel b	X	X			X	X	X	X
HCC Assessment: Liver Ultrasound c			X			X	X	X
HCC Assessment: Alpha fetoprotein c			X		X	X	X	X
Concomitant Medication Assessment d	X	X	X	X	X	X	X	X
Adverse Event Assessment e	X	X	X	X	X	X	X	X
HCV RNA Samples	X	X	X	X	X	X	X	X
HCV Resistance Sample f	X	X	X	X	X	X	X	X
Patient Reported Outcome g		X						X g
HIV RNA Samples h	X	X						
Flow Cytometry h	X							

D/C = Discontinuation

- a. A positive urine pregnancy test requires a confirmatory serum test. (Refer to Section 5.3.1.1 [Pregnancy Test] for additional details.) Females who are experiencing menses or are nearing sexual maturation in the opinion of the PI or who are of childbearing potential should have urine pregnancy testing done through Post-Treatment Week 4. Pregnancy testing will be performed at PT Premature D/C visit only if the subject discontinues prior to PT Wk 4.
- b. Urinalysis will not be conducted after the Post-Treatment Week 4 visit. Urinalysis will be performed at PT Premature D/C visit only if the subject discontinues prior to PT Wk 4. The coagulation panel will be obtained at PTW4 for all patients. For non-cirrhotic subjects: Perform the coagulation panel at visits only if clinically indicated after post treatment Week 4.
- c. HCC assessment for subjects with compensated cirrhosis only.

- d. Concomitant medication will be collected for 30 days after study drug has been stopped, thereafter only antiviral medicines taken for the treatment of HCV and medications taken for SAEs will be recorded. See section 5.2.3.
- e. Non-serious AEs and all SAEs will be collected until 30 days post dosing. Only spontaneously reported SAEs will be collected thereafter. See Section 6.1.
- f. Resistance samples are only collected for patients that meet virologic failure criteria and should be drawn at the confirmatory visit, and if confirmed, at all subsequent visits.
- g. The PRO should be administered as the first study procedure. PRO will be accessed at the Premature D/C visit only if the subject discontinues prior to PT Wk 12.
- h. Only applicable for HCV/HIV-1 co-infected subject.

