**Table 6. Treatment Regimen and Duration (Subjects in Japan)**

Patient Population	Duration
GT1 – 2 NC, TN, TE – IFN	8 weeks
GT1 – 2 C, TN, TE – IFN GT3 – 6 NC, C, TN, TE – IFN GT1 – 6 TE – SOF	12 weeks

Legend: C = Cirrhotic; NC = Non-Cirrhotic; TE – IFN = Japan Treatment experienced to IFN (alpha, beta or pegIFN) ± RBV; TE – SOF = Japan Treatment experienced to SOF/RBV; TN = Treatment Naïve

GLE/PIB will be administered as described in Section 5.5.1 (Treatments Administered). Subjects and their parent(s)/guardian(s) will receive instructions about the study drugs at the Day 1 Visit. The study drugs will be dispensed at the visits as indicated in [Appendix C](#).

After the Day 1 visit, all subjects will continue to return to the site on an outpatient basis for the study visits and procedures as identified in [Appendix C](#). Subjects could also return to the site for an unscheduled study visit for additional safety assessments if the investigator or sponsor feels it is necessary. Sites should ensure that subjects adhere to the study visits listed in [Appendix C](#). Subjects who cannot complete their study visit per the visit schedule should ensure they do not run out of study drug prior to their next study

visit. Study drug compliance is critical to ensure adequate drug exposure and optimal treatment outcome.

Virologic failure criteria will be evaluated and applied by the Investigator as detailed in Section 5.4.1.1.

Subjects who prematurely discontinue from the Treatment Period should return for a Treatment Discontinuation Visit and undergo the study procedures as outlined in [Appendix C](#) and as described in Section 5.5.1. Ideally, this should occur on the day of study drug discontinuation, but is recommended to be no later than 2 days after their final dose of study drug and prior to the initiation of any other anti-HCV therapy if applicable. Following completion or premature discontinuation of study drug treatment, all subjects in either Part 1 or Part 2 will be followed in the associated Post-Treatment Period of Part 1 or Part 2.

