### **HCV Resistance Testing Plasma Sample**

A plasma sample for baseline HCV resistance testing will be collected on Day 1 from all subjects in Part 1, and from subjects in Part 2 in which the sample for baseline HCV resistance testing will be within the allowable blood volume limits. HCV resistance testing is required for all subjects who meet virologic failure criteria at the visits indicated in [Appendix C](#). Specific instructions for preparation and storage of the samples will be provided by the central laboratory, the Sponsor, or its designee.

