#### **5.4.1.1 HCV Virologic Failure Criteria**

The following criteria will be considered evidence of HCV virologic failure for the purposes of subject management:

- Confirmed increase from nadir in HCV RNA (defined as 2 consecutive HCV RNA measurements of  $> 1 \log_{10}$  IU/mL above nadir) at any time point during treatment; or
- Confirmed HCV RNA  $\geq 100$  IU/mL (defined as 2 consecutive HCV RNA measurements  $\geq 100$  IU/mL) after HCV RNA  $<$  LLOQ during treatment.

When confirmatory testing is required it should be completed as soon as possible and the subject should remain on study treatment until the HCV virologic failure criterion has been confirmed. Subjects meeting a virologic failure criterion will be discontinued from

study drug and will continue to be followed in the Post-Treatment Period for the emergence and persistence of resistant viral variants until 144 weeks post-treatment.

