### **8.1.6 Resistance Analysis**

#### **8.1.6.1 HCV Drug-Resistance Analyses**

The secondary endpoint of resistance associated viral variants will be analyzed as follows. For all subjects in Part 1 and subjects with available samples in Part 2, full length NS3/4A or NS5A from baseline samples will be sequenced by NGS. For all subjects who experience virologic failure (on-treatment virologic failure or post-treatment relapse), full length NS3/4A and NS5A genes from the first sample after virologic failure with HCV RNA  $\geq 1000$  IU/mL will be sequenced by NGS. An appropriate subtype-specific prototypic reference sequence will be used for comparison with sequences from samples. Subjects treated with study drug who do not achieve SVR12 due to reasons other than virologic failure but have a time point with HCV RNA  $\geq 1000$  IU/mL after treatment discontinuation, will have the sample at that time point sequenced.

Only samples with an HCV RNA level of  $\geq 1000$  IU/mL will undergo sequence analysis in order to allow accurate assessment of products of amplification. Therefore, if the HCV RNA level at the time of HCV virologic failure or treatment discontinuation is  $< 1000$  IU/mL, the sample closest in time after HCV virologic failure/treatment discontinuation with an HCV RNA level  $\geq 1000$  IU/mL will be used. Included time

points for analyses on samples from subjects who do not achieve SVR12 are 1) the sample closest in time after failure/discontinuation with an HCV RNA level of  $\geq 1000$  IU/mL, and 2) 24 weeks post-DAA treatment, provided that resistance-associated substitutions were detected by NGS at the time of HCV virologic failure/treatment discontinuation.

For each DAA target, signature amino acid positions and a key subset of amino acid positions are listed in [Table 12](#). Appropriate subtype specific prototypic reference sequence will be used for comparison with sequences from samples.

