HCV reinfection is defined as confirmed HCV RNA \geq LLOQ after the end of active treatment in a subject who had HCV RNA $<$ LLOQ at Final Treatment Visit, along with the post-treatment detection of a different HCV genotype, subtype, or clade compared with baseline, as determined by phylogenetic analysis of the NS3 or NS5A, and/or NS5B gene sequences. Reinfection in the case of the same HCV subtype is defined as a clade switch, as indicated by the lack of clustering between the baseline and post-treatment sequences by phylogenetic analysis. If phylogenetic analysis is not possible due to technical difficulties, HCV reinfection may be determined with a confirmed HCV genotype or subgenotype switch by the Versant HCV Genotype Inno-LiPA Assay v2.0 or Sanger assay.

Post-treatment relapse is defined as described earlier (**Relapse₁₂**, **Relapse₂₄**, **Relapse_{overall}**), and no genotype, subtype, or clade switch compared with baseline as determined by phylogenetic analysis of the NS3 or NS5A gene sequences. If phylogenetic analysis is not possible due to technical difficulties, the subject will be defined as having a post-treatment relapse unless an HCV genotype or subtype switch is confirmed by the Versant HCV Genotype Inno-LiPA Assay v2.0 or Sanger assay.

Reasons for SVR₁₂ Non-Response

Subjects who do not achieve SVR₁₂ (SVR₁₂ non-responders) will be categorized as having:

1. On-treatment virologic failure (see **On-treatment virologic failure** definition);

2. HCV reinfection (see definition described earlier);
3. Relapse₁₂;
4. Prematurely discontinued study drug with no on-treatment virologic failure (defined as any SVR₁₂ non-responder who prematurely discontinued study drug [study drug duration < 52 days for subjects assigned to 8 weeks of treatment, < 77 days for subjects assigned to 12 weeks of treatment, and < 103 days for subjects assigned to 16 weeks of treatment] and did not meet the **On-treatment virologic failure or reinfection** definitions);
5. Missing follow-up data in the SVR₁₂ window (defined as any subject who completed study drug without data in the SVR₁₂ window after applying the imputation rules and not meeting the definitions of [1], [2], [3], or [4]);
6. Other (defined as any SVR₁₂ non-responder not meeting the definitions of [1] – [5]).

Reasons for SVR₂₄ Non-Response

Subjects who do not achieve SVR₂₄ (SVR₂₄ non-responders) will be categorized as having:

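### The sampling rule gives no resistance sample to SVR12 non-responders without virologic failure whom the plan means to sequence, and leaves the trigger for relapsers inconsistent

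*Protocol*

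**What the plan says.** **Collection.** Protocol Appendix C, Post Treatment Period, note f: "Resistance samples are only collected for patients that meet virologic failure criteria and should be drawn at the confirmatory visit". Section 5.3.1.1 (HCV Resistance Testing Plasma Sample) has the same condition: "HCV resistance testing is required for all subjects who meet virologic failure criteria at the visits indicated in" Appendix C. Neither place defines the criteria, and nor does note t to the treatment-period schedule.

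**Criteria.** Section 5.1.2 says "Virologic failure criteria will be evaluated and applied by the Investigator as detailed in Section 5.4.1.1". Section 5.4.1.1 opens with "The following criteria will be considered evidence of HCV virologic failure for the purposes of subject management" and lists two events: a confirmed rise of more than 1 log10 above nadir, and a confirmed value of at least 100 IU/mL after a value below LLOQ. Both are limited to the time on treatment.

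**Analysis.** Section 8.1.6.1 plans "For all subjects who experience virologic failure (on-treatment virologic failure or post-treatment relapse), full length NS3/4A and NS5A genes from the first sample" after failure with HCV RNA of at least 1000 IU/mL. It adds that a subject who misses SVR12 for a reason other than virologic failure, but has such a value after stopping treatment, "will have the sample at that time point sequenced". SAP 10.8.1 repeats this and names the reasons: premature discontinuation, reinfection, missing SVR12 data, or other. SAP 10.1 defines reinfection as confirmed post-treatment viraemia "along with the post-treatment detection of a different HCV genotype, subtype, or clade compared with baseline".

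**The concern.** The collection rule and the analysis rule cover different sets of children. Note f contains the word only, so a site that follows it draws nothing from a child outside the failure criteria, even when the analysis section expects a sequence from that child. The sole list that investigators are told to apply is an on-treatment one.

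Three secondary items depend on a post-treatment sequence: emergence and persistence of resistant variants, relapse, and reinfection. Blood that was not drawn cannot be recovered later. The documents do not say whether plasma taken for HCV RNA may be sequenced instead.

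**Working it through.** There is no plan figure to reproduce. The check sets the passages side by side and then gauges scale.

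**1. Who is to be sequenced, and who has a trigger**

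| SVR12 non-responder | Sequencing planned (8.1.6.1, SAP 10.8.1) | Meets 5.4.1.1 | Virologic failure elsewhere in the protocol | Trigger under note f |
|---|---|---|---|---|
| Breakthrough on treatment | Yes | Yes | Yes (8.1.2.2) | Clear |
| Quantifiable at end of treatment, never below LLOQ, no rise above 1 log10 | Yes | No | Yes (8.1.2.2, with at least 6 weeks of treatment) | Inconsistent |
| Relapse after completed treatment | Yes | No | Yes (8.1.6.1) | Inconsistent |
| Reinfection after completed treatment | Yes (SAP 10.8.1) | No | Looks like relapse until sequenced | Inconsistent |
| Stops early below LLOQ, then rebounds to 1000 IU/mL or more | Yes | No | No | None |

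The last row follows from the definitions. Relapse in 8.1.2.2 and SAP 10.1 requires completed treatment: at least 52, 77 or 103 days for the 8-, 12- and 16-week regimens. A child who stops sooner and rebounds is neither an on-treatment failure nor a relapse. Section 5.4.1 nevertheless says that subjects who discontinue study drug are monitored post-treatment for resistant substitutions, so note f conflicts with 5.4.1 as well.

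**2. What a missed sample does to classification**

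SAP 10.1 separates reinfection from relapse by phylogenetic analysis. If that is not possible for technical reasons, the child is a relapse unless Inno-LiPA or Sanger shows a genotype or subtype switch. A same-subtype reinfection shows no such switch. If a missing sample is handled the same way, that child is counted as a relapse. The Inno-LiPA or Sanger route also needs a post-treatment sample, and Appendix C schedules genotyping at Screening only.

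**3. Scale**

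Inputs: adult TN plus TE-PRS SVR12 of 2206/2256 (protocol Table 3); 23 virologic failures in TN and TE-PRS adults, one later shown to be a reinfection (protocol 3.0); about 125 children (8.2). The 23 are assumed to come from the same 2256.

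- Non-responders: 2256 − 2206 = 50. Others: 50 − 23 = 27, or 50 − 22 = 28 with the reinfection moved across.
- Expected non-responders in 125: 125 × 50/2256 = 2.77.
- Expected virologic failures: 125 × 23/2256 = 1.27, or 125 × 22/2256 = 1.22.
- Expected other non-responders: 125 × 27/2256 = 1.50, or 125 × 28/2256 = 1.55.
- Chance of at least one virologic failure: 1 − (1 − 23/2256)^125 = 0.72.
- Chance of at least one other non-responder: 1 − (1 − 27/2256)^125 = 0.78.

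The documents do not split adult failures into on-treatment and relapse. They also do not say how many of the other non-responders were viraemic.

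**The case against.** The strongest counter-case is that note f does not cite 5.4.1.1, and that 5.4.1.1 describes itself as a subject-management rule. Section 8.1.6.1, in the same protocol, counts relapse as virologic failure, and the SAP agrees. Note f sits in the post-treatment table and says samples "should be drawn at the confirmatory visit, and if confirmed, at all subsequent visits". On-treatment failure is normally confirmed before that period begins, so a post-treatment confirmatory visit makes most sense if relapse is a trigger. The resistance row is marked at every post-treatment visit, and Appendix D allows 6.0 mL for the sample. These two features are weaker evidence, because on-treatment failures are themselves followed for resistance to Week 144.

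This argument stands for relapsers and for reinfected children, who look the same when blood is drawn. A reader might infer that these children have no sample to sequence. The documents do not support that. They show a term used in two senses in site-facing text, with a risk of missed draws.

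A reader might also infer that the 48-week gaps between late visits call for extra unscheduled visits. The relapse endpoint closes with the SVR12 window, with visits at Post-Treatment Weeks 4, 12 and 24 around it. SAP 10.1 also counts a last available value at or above LLOQ as relapse without confirmation. Extra visits are not needed.

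The counter-case does not reach the non-responders without virologic failure. The monitoring statement in 5.4.1 contradicts note f but supplies no draw. Much of the resistance analysis is conditional on available samples, but that does not justify a rule that stops them being collected.

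**Conclusion.** The point holds in two parts. For SVR12 non-responders without virologic failure, note f conflicts with 8.1.6.1, SAP 10.8.1 and 5.4.1: sequencing is planned and no collection is triggered. For relapsers, reinfected children and end-of-treatment failures, the trigger is inconsistent, so samples may be missed, and a same-subtype reinfection may be reported as relapse.

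The number of children is small: about 2.8 expected non-responders in all. That figure rests on adult rates carrying over to children, and the viraemic share of those without virologic failure is unknown. Because so few are expected, one missed sample could be much of the resistance evidence. The primary AUC endpoint, the SVR12 rate and the safety analyses are not affected. The passages should be reconciled while samples can still be drawn.

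**What to change.** For sampling only, in Appendix C notes t and f and in 5.3.1.1, set the trigger as either:

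- (a) on-treatment failure per 5.4.1.1; or
- (b) HCV RNA at or above LLOQ at the end-of-treatment or premature discontinuation visit, or at any post-treatment visit, whatever the presumed reason.

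Under (b), draw the resistance sample at the repeat or next visit and, if viraemia is confirmed, at later visits. Including every post-treatment visit matches 8.1.2.2, which counts reinfection up to the last visit. Alternatively, state that stored HCV RNA plasma from the visit may be sequenced. That also covers a last quantifiable value with no later visit. State that 5.4.1.1 is unchanged as the subject-management rule.

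The cost is protocol wording and a 6.0 mL draw per sampled visit in the few children with quantifiable HCV RNA. Appendix D states that allowance in the post-treatment tables only, so any draw made within the treatment period would have to be added and checked against the blood-volume limits that 5.3.1.1 already applies to the baseline sample in Part 2. Some samples will be below 1000 IU/mL and will not be sequenced.
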